### 7.5. Analysis Windows

For all measures that are summarized by visit, analysis visits will be assigned based on the analysis windows provided in Table 4. If more than one assessment falls into an assessment window, the assessment that is closest to the target day will be picked. If more than one assessment is equidistant from the target day, the earlier time will be picked.

Analysis windows are selected based on the midpoint between the upper bound of the previous window and the lower bound of the following window based on the protocol defined windows.

Analysis visits will be used in all summaries, figures, and efficacy analyses. Listings will not use analysis visits and instead use nominal visits based on the data. End of study visit will be summarized as a nominal visit as well as the analysis visit for which it falls under.

Nominal Visit (Target Day)	Protocol Window	Analysis Window
0	0	≤0
7	[6, 8]	[1, 10]
14	[13, 15]	[11, 22]
30	[28, 32]	[23, 42]
60	[53, 67]	[43, 75]
90	[83, 97]	[76, 105]
120	[113, 127]	[106, 135]
150	[143, 157]	[136, 165]
180	[173, 187]	[166, 195]
210	[203, 217]	[196, 225]
240	[233, 247]	[226, 252]
270	[256, 284]	≥253

Table 4:Analysis Windows

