### 6. STUDY DESIGN

## 6.1. Description of the Study

This is a Phase 2a, safety and efficacy study of XT-150 in adult participants experiencing back pain due to inflammation of the facet joint (Facet Joint Osteoarthritis [FJOA]) and who are eligible for intra-articular glucocorticoid injection, or radiofrequency ablation of medial branches of the primary dorsal ramus of the exiting nerve root, which innervates the adjacent facet joints.

Participants will provide informed consent and meet all study eligibility criteria before any study procedures are initiated. Baseline assessments for study eligibility will be completed on the same day as or within 1 day before administration of study drug.

Study drug will be administered at Day 0 and Day 90 by intra-articular (IA) injection into the facet capsules, bilaterally at the affected spinal level (e.g. L4-5 and L5-S1). Location responsible for facetogenic pain of the spine will be determined by clinical, radiological and diagnostic (lidocaine) intra-articular injection.

Up to 72 participants will be randomized to one of two dose treatment groups or to placebo (24 participants per treatment group).

- 1. 150 μg XT-150 (1.0 mL total delivered by two 0.5 mL injections)
- 2. 450 µg XT-150 (1.0 mL total delivered by two 0.5 mL injections)
- 3. Placebo (Sterile phosphate-buffered saline for injection, PBS) (1.0 mL total delivered by two 0.5 mL injections).

Following the first treatment with XT-150 or Placebo at Baseline (Day 0), participants will be assessed for safety and efficacy in-clinic on Days 7, 14, 30 and 60. At Day 90, all participants will receive a repeat injection with XT-150 or Placebo based on treatment arm assignment at the time of randomization. Following Day 90, participants will be assessed approximately monthly through Day 270.

Participants who have passed their Day 90 visit or who were enrolled prior to the implementation of Protocol V3.0 08Jun2022 and do not reconsent to a second dose will complete the study at Day 180. During this visit, all End of Study visit activities should be completed.

The Schedule of Assessments and Procedures is presented in Table 1. Day 0 is defined as the day of study drug administration. Subsequent study days are defined by the number of consecutive calendar days after drug administration.

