### 7. STATISTICAL METHODS

#### 7.1. General Considerations

#### 7.1.1. Standard Calculations

- Variables requiring calculation will be derived using the following formulas:
- Baseline: A baseline value, unless specified otherwise, is the last non-missing value recorded prior to the first dose of study drug (or placebo) on Day 0 as defined in the protocol (analysis Day 1). If an assessment has both a date and time that exactly match the date and time of first dose of study drug, the assessment will be counted as baseline.
- Change from Baseline: Change from baseline will be calculated for each participant at the specified time point as the value at the specified time point minus the baseline value.
- Study day: In the protocol, Day 0 is defined as the day of study drug administration. Subsequent study days are defined by the number of consecutive calendar days after drug administration. However, CDISC standards require the first day of study drug administration to be Day 1 and therefore, study day will be calculated differently as outlined below for display in tables, figures, and listings (TFLs):
  - Study day = date dose date + 1, where date  $\geq$  dose date
  - Study day = date dose date, where date < dose date
- Days: Durations, expressed in days, between one date (date1) and another later date (date2) are calculated according to the following formula: duration in days = (date2 date1 + 1).
- Body Mass Index (BMI): BMI (kg/m2) = weight (kg) / [[height (cm)/100]2].

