#### **10.14.3.** Clinical Examination of the Back (Injection Site)

Clinical examinations of the back and injection site will be performed regularly during the study. The following examination criteria will be assessed and the proportion of participants with symptoms will be summarized by visit:

- Pain
- Erythema
- Swelling
- Pruritus
- Warmth
- Hematoma
- Induration
- Other skin reactions

Injection site reactions will also be recorded as AEs.

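### SAP 7.5 counts visit windows from dose 1 only, so after a second dose on Days 83 to 89 an unscheduled assessment can replace the pre-dose Day 90 value

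*SAP*

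**What the plan says.** SAP 7.5 (Table 4) fixes the Day 90 analysis window at Days 76 to 105 and the Day 120 window at Days 106 to 135. The construction rule is "Analysis windows are selected based on the midpoint between the upper bound of the previous window and the lower bound of the following window". Within a window, "If more than one assessment falls into an assessment window, the assessment that is closest to the target day will be picked", and for ties "If more than one assessment is equidistant from the target day, the earlier time will be picked". The scope is wide: "Analysis visits will be used in all summaries, figures, and efficacy analyses". Listings keep nominal visits.

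The time anchors are all at the first dose. On study day, SAP 7.1.1 notes that "CDISC standards require the first day of study drug administration to be Day 1". It defines baseline as "the last non-missing value recorded prior to the first dose of study drug (or placebo) on Day 0". No second baseline is defined.

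Dose 2 belongs to the Day 90 visit. Protocol 6.1 states: "At Day 90, all participants will receive a repeat injection with XT-150 or Placebo based on treatment arm assignment". Protocol 9.4 gives that visit a window of ±7 days. It lists VAS, the other questionnaires, vital signs and an injection-site examination ahead of dosing. A further injection-site check is listed with dosing, and vital signs about 1 hour after it. For the injection-site examination, SAP 10.14.3 says that "the proportion of participants with symptoms will be summarized by visit".

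**The concern.** SAP 8 says that the second dose added by protocol version 3.0 has been taken up in the SAP, yet the visible window rule does not mention it. The Day 90 window extends at least 8 days beyond any permitted dose-2 day, and proximity to Day 90 alone decides which assessment is used. A value recorded after the second injection can therefore stand in the Day 90 row in place of the value recorded just before it.

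This matters because the primary objective is the safety and tolerability of a repeat dose. SAP 10.14.1 counts treatment-emergent events from the first dose, and the tables it lists are not split by dose. The by-visit tables are thus the main visible summaries that separate the time before dose 2 from the time after it.

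No visit is scheduled between Day 90 and Day 120. Any assessment from the day after dose 2 to Day 105 either displaces the pre-dose value or is not selected, and Table 4 has no row that shows it as a post-dose-2 finding. Unscheduled visits may be prompted by symptoms, so displacement need not be random.

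**Working it through.** **Inputs.** Protocol visit windows and analysis windows: SAP Table 4. Selection and tie rules: SAP 7.5. Permitted dose-2 days 83 to 97: Protocol 9.4 (90 ± 7). Days are counted as in the protocol, with first dosing on Day 0.

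**1. Reproducing Table 4.** Upper limit = (upper protocol limit of the visit + lower protocol limit of the next visit) / 2. For Day 60: (67 + 83)/2 = 75. For Day 90: (97 + 113)/2 = 105. For Day 120: (127 + 143)/2 = 135. Over Days 7 to 240 the formula gives 10.5, 21.5, 42.5, 75, 105, 135, 165, 195, 225 and 251.5. Table 4 has 10, 22, 42, 75, 105, 135, 165, 195, 225 and 252. All ten agree if halves are rounded to the even integer, and the limits of the Day 90 window need no rounding. The dose-2 date does not enter.

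**2. A post-dose-2 value taken as Day 90.** Let the pre-dose assessment and dose 2 fall on day d, and an extra assessment on a later day u. The later one is selected if |u − 90| < |d − 90|. For d < 90 this means d < u < 180 − d, which gives 179 − 2d days.

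| Dose-2 day d | Days u that displace the pre-dose value | Number of days |
|---|---|---|
| 83 | 84 to 96 | 13 |
| 84 | 85 to 95 | 11 |
| 85 | 86 to 94 | 9 |
| 86 | 87 to 93 | 7 |
| 87 | 88 to 92 | 5 |
| 88 | 89 to 91 | 3 |
| 89 | 90 | 1 |
| 90 to 97 | none | 0 |

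Example: with dose 2 on Day 84 (distance 6) and an unscheduled visit on Day 91 (distance 1), Day 91 is reported as Day 90.

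**3. Pre-dose value missing.** Any assessment up to Day 105 then fills the slot. The longest delay after dose 2 is 105 − 83 = 22 days for dosing on Day 83 and 105 − 97 = 8 days for dosing on Day 97.

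**4. Same-day values.** Pre-dose and post-dose readings on one day are equally distant from Day 90, so the tie rule keeps the earlier one, which is the pre-dose reading.

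**5. A pre-dose-2 value taken as Day 120.** The value must fall on Day 106 or later. No dose-2 day from 83 to 97 does so, and 106 − 97 = 9 days past the limit is the minimum. For d up to 120, the pre-dose value is selected over a later visit v only if v ≥ 240 − d (v > 120 when d = 120). For d = 106 that is Day 134 or later, and for d = 112 Day 128 or later. For dose 2 on Days 106 to 112, a Day 120 visit inside its own window (113 to 127) always wins, so that visit must be missed or late. Only dose 2 on Days 113 to 126 can displace some in-window Day 120 visits.

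**6. Day-count convention.** If Table 4 is applied to the SAP study day (first dosing = Day 1), step 2 covers dose-2 protocol Days 83 to 88. Step 5 then starts at protocol Day 105. The conclusion does not change.

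**7. Weight of one participant.** With 24 per arm (SAP 5.2), one misplaced finding moves a by-visit proportion by 1/24, about 4 percentage points.

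**The case against.** The strongest reply is that little rests on the Day 90 row. Injection-site events must also be recorded as adverse events (Protocol 10.7.2, SAP 10.14.3), and Grade 2 or higher reactions are events of special interest with their own table and listing. None of those tables is windowed. The Day 270 endpoint uses Day 253 onward and is untouched. No visible section labels Day 90 as the last pre-dose-2 value or compares it with Day 120. All of this stands, and it limits the point to descriptive by-visit summaries.

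The trigger is also uncertain. Displacement needs an extra assessment that the schedule does not provide, although Protocol 9 allows nonscheduled safety procedures and SAP 10.14.2 mentions unscheduled visits. Protocol 11.1.1 collects VAS at study visits, and nothing schedules it at unscheduled ones, so VAS is exposed only if it happens to be taken. SAP 10.14.4 summarizes vital signs at scheduled time points and could be read as leaving out unscheduled readings, but 7.5 makes no such exclusion. Summaries by timepoint (SAP 7.1.2) can separate readings within a visit but do not settle which of two days is chosen.

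A reader might infer that the opposite error is equally likely, with one-dose data reported as Day 120. The documents do not support that. It cannot occur while dose 2 is inside its window; it usually needs a missed or late Day 120 visit as well; and no visible text provides for dosing after Day 97.

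A reader might also see misassignment in the spread from dose 2 to an in-window Day 120 visit, 113 − 97 = 16 to 127 − 83 = 44 days. That is the ordinary result of two ±7-day windows.

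Finally, SAP 7.4 and parts of 10.13 cannot be read in the public copy. The VAS section breaks off in a sentence about participants who receive a single dose. A relevant rule may stand there.

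**Conclusion.** The point holds for the visible text of SAP 7.5. With dose 2 given inside its protocol window on Days 83 to 89, and without any protocol deviation, there are 13 down to 1 later days on which an extra assessment would replace the pre-dose value. It would do so in the Day 90 summaries of injection-site findings, vital signs and any questionnaire collected. A missing pre-dose value opens the slot to anything up to Day 105, for every permitted dosing day. Entry of a pre-dose-2 value into Day 120 is a secondary edge case outside the protocol window.

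The conclusion assumes that unscheduled assessments enter the windows, which 7.5 does not exclude, and that no unreadable section overrides the rule. The documents give no rate of off-target dosing, missing pre-dose values or unscheduled assessments, so the number of participants affected cannot be computed. This is a cheap improvement to the by-visit safety and efficacy summaries. It does not threaten the adverse event analysis or the Day 270 endpoint.

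**What to change.** Add to SAP 7.5:

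> For participants given dose 2, only assessments made on or after Day 76 and before the date and time of dose 2 are eligible for the Day 90 analysis visit; if there is none, Day 90 is missing. The scheduled 1-hour post-dose vital signs are shown as a Day 90 post-dose timepoint. Other assessments after dose 2 up to Day 105 are summarized in a separate post-dose-2 unscheduled row. Only assessments after dose 2 are eligible for the Day 120 and later windows; pre-dose-2 assessments made after Day 105 are listed only.

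Participants without dose 2 keep Table 4 as it stands. The lower bound at Day 76 prevents a Day 60 value from being carried into Day 90, in line with the no-imputation rule of SAP 7.3. Protocol 9.4 does not say whether the injection-site check listed with dosing precedes or follows the injection. If it follows, show it as a Day 90 post-dose timepoint too.

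For dosed participants with recorded dates and times, this removes both misassignments by construction. The cost is a short SAP addition, one dataset flag and one extra table row, with no new data. The downside is that a few Day 90 values may become missing.

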## 5.1.2. Secondary Objectives

The secondary objective is to establish the analgesic efficacy of a repeat bilateral intra-articular dose of XT-150 as a treatment for pain in participants with facet joint osteoarthritis (FJOA).

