## 7.4. Participant Withdrawal Criteria

## 7.4.1. Withdrawal from Study Protocol

Participants who wish to withdraw completely from this clinical study should be encouraged to complete the assessments for Day 270/Termination. However, participants may withdraw consent to participate in this study at any time without penalty or loss of benefits to which the participant is otherwise entitled. Every reasonable effort should be made to determine the reason a participant withdraws prematurely, and this information should be recorded on the appropriate page(s) of the case report form (CRF). Participants may be withdrawn from the study for any of the following reasons:

- Participant unable or unwilling to continue
- Participant's perceived lack of benefit
- Participant elects to withdraw informed consent
- Due to an adverse event
- Protocol non-compliance
- Participant is lost to follow up
- The PI considers that it is in the participant's best interest not to continue participation in the study

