## 9.5. Between Clinic Visits

# 9.6. Follow Up Visits – Day 7 (±1 day), Day 14 (±1 day), Day 30 (±2 Days), Day 60 (±7 days), Day 120 (±7 days), Day 150 (±7 days), Day 180 (±7 days), Day 210 (±7 days) and Day 240 (±7 days)

Participants who were enrolled in the study prior to implementation of Protocol Version 3.0 08Jun2022 and either are past their Day 90 visit or do not consent to the Day 90 repeat dose will have their End of Study Visit at Day 180. In this situation, participants should complete all of the End of Study / Day 270 Assessments. Refer to Section 9.7.

- Clinical assessments
  - Brief physical exam, including the injection site for infections or inflammation
  - Measure vital signs (temperature, heart rate, blood pressure, and respiratory rate)
- Efficacy assessments
  - VAS score
  - Oswestry Disability Index
  - IPAQ short form
  - SF12
  - Record participant's response to the question: "Considering all the ways that
    Facet pain, the pain that brought you into this study, affects you, how are you
    doing today?" on a scale of 1 to 5, 1 being very good (asymptomatic and no
    limitation of normal activities) to 5, very poor (very severe, intolerable symptoms
    and inability to carry out normal activities)
  - Record changes in drug regimens or pain therapy
- Laboratory assessments
  - Days 7 (±1 day), 14 (±1 day), and 30 (±2 days): Obtain whole blood for analysis of XT-150 plasmid DNA analysis
  - Days 7 (±1 day), 14 (±1 day), 30 (±2 days), 60 (±7 days), and 180 (±7 days):
     Obtain serum for analysis of IL-10 protein and anti-IL-10 antibodies
- Assess, identify, and record any AEs since last visit
- Record any changes in concomitant medications since screening visit including prescription, OTC, and herbal medications.

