### 8. PROTOCOL VERSION 3.0 ANALYSIS IMPACT

Protocol version 3.0, dated June 8, 2022, made significant changes to the study design including adding a 2nd dose of study drug and two interim analyses. These changes are reflected in the SAP.

Due to this protocol version occurring during the study, some participants will receive only a single injection at baseline and complete the study at day 180 instead of day 270 as per the protocol prior to v3.0 if they did not sign informed consent for v3.0. In effect they will not complete the study under protocol v3.0 and will be considered pre-3.0 participants. These participants will be included in the ITT and Safety populations (if applicable) but will be excluded from the PP population.

Summary tables of the ITT and Safety populations will combine pre-3.0 and post-3.0 participants. Informed consent, disposition, and randomization tables and listings will delineate those who were considered pre-3.0 and those who were post-3.0.

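### By-visit ITT and Safety summaries at Days 120, 150 and 180, and the End of Study row, mix one-dose and two-dose participants and so do not describe the repeat-dose regimen

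*SAP*

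**What the plan says.** The change of design during the trial left two groups. SAP 8 explains that "some participants will receive only a single injection at baseline and complete the study at day 180 instead of day 270". Protocol 9.6 says of participants enrolled before v3.0 who are already past Day 90, or who decline the second dose, that they "will have their End of Study Visit at Day 180" and do all end-of-study assessments then. The others are to be re-injected at Day 90 and followed to Day 270.

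On tabulation, SAP 8 says of the pre-3.0 group: "These participants will be included in the ITT and Safety populations (if applicable) but will be excluded from the PP population". It continues: "Summary tables of the ITT and Safety populations will combine pre-3.0 and post-3.0 participants". The separation it does promise is limited to certain outputs: "Informed consent, disposition, and randomization tables and listings will delineate those who were considered pre-3.0 and those who were post-3.0".

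SAP 7.5 places each assessment in an analysis visit by day window, and adds: "End of study visit will be summarized as a nominal visit as well as the analysis visit for which it falls under".

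The secondary objective in Protocol 5.1.2 is "to establish the analgesic efficacy of a repeat bilateral intra-articular dose of XT-150". The primary objective, in Protocol 5.1.1 and SAP 4.1, is safety and tolerability of the same repeat dose.

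**The concern.** Both objectives are about a second injection. After Day 90, a summary row that includes people who never had that injection describes a blend of two regimens. Any added benefit of dose 2 is diluted, and so is any added harm. For the primary objective this matters most in the injection-site and vital-sign tables, where re-injected people are averaged with people who were not re-injected.

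The End of Study row adds a second mixture, because the label stands for different study days and different numbers of doses. The blend can also differ by arm: participants enrolled before v3.0 and not yet at Day 90 chose whether to take dose 2 after experiencing dose 1.

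**Working it through.** 1. **The plan's own figure.** Protocol 14.1 gives a 95% interval of about 29% to 71% for a 50% responder rate in one arm. The exact (Clopper-Pearson) interval for 12 of 24 is 29.1% to 70.9%, so it reproduces. The documents give no power or effect size to check. The interval is used in step 6 as a yardstick for precision.

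2. **Which visits are mixed.** One-dose participants leave at Day 180, with protocol window 173 to 187. SAP Table 4 maps Days 166 to 195 to the Day 180 row, so an in-window final visit lands there. It would have to fall after Day 195 to reach the Day 210 row. SAP 7.3 does not impute missing continuous values. Observed-value mixing therefore occurs at Days 120, 150 and 180, which is 3 of the 6 scheduled visits after Day 90.

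3. **What the Day 180 row combines.** One-dose participants are 173 to 187 days after their only dose. With dose 2 given on Days 83 to 97, two-dose participants are 173 − 97 = 76 to 187 − 83 = 104 days after their second.

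4. **What the End of Study row combines.** Measured from the first dose, it holds Days 173 to 187 (one dose) and Days 256 to 284 (two doses). Measured from the last dose, it holds 173 to 187 days and 256 − 97 = 159 to 284 − 83 = 201 days. Protocol 7.4.1 also says that people who withdraw "should be encouraged to complete the assessments for Day 270/Termination". If those visits are entered as End of Study, they can fall on any day.

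5. **Dilution at Days 120 to 180.** Let s be the share of an arm that received dose 2, and δ the VAS change that dose 2 adds. The pooled arm mean is the one-dose mean plus sδ.
   - With equal s in both arms, the between-arm increment (δ active − δ placebo) is multiplied by s.
   - Assume an increment of 10 points. With 7 of 72 one-dose, s = 65/72 = 0.90, giving 9.0 points. With 24 of 72, s = 48/72 = 0.67, giving 6.7 points.
   - The counts are assumptions: 7 is borrowed from the threshold in the cut-off line of the SAP's VAS section, and 24 is an illustrative third of the sample.
   - If s differs by arm, the contrast becomes s(active) × (δ active − δ placebo) + (s(active) − s(placebo)) × δ placebo. The second term is bias that remains even when dose 2 adds the same in both arms.
   - Put another way, suppose the one-dose effect at Day 180 is 0 to 50% of the two-dose effect (fraction r) and k of 24 per arm are one-dose. The pooled effect is 1 − (k/24)(1 − r) of the two-dose effect: 91.7% to 95.8% at k = 2, 75.0% to 87.5% at k = 6, and 50% to 75% at k = 12.

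6. **Precision of a two-dose row.** With 24 − k per arm and a 50% rate, the exact interval is 28.2% to 71.8% at k = 2, 24.7% to 75.3% at k = 8, and 21.1% to 78.9% at k = 12. Showing the two-dose group separately costs little precision unless k is large.

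**The case against.** **The primary endpoint is untouched.** This stands. A reader might infer that the pooling runs through every visit after Day 90 and so contaminates the Day 270 VAS result. The documents do not support that: planned Day 180 completers supply no scheduled values at Days 210, 240 or 270, and continuous values are not imputed. Two side routes exist but lie outside this point. A participant who missed the Day 90 injection yet stayed to Day 270 would be a one-dose case there. SAP 7.3 also counts missing as not improved in the VAS responder analyses, which could keep one-dose participants in later denominators; the section describing those analyses is not readable.

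**The plan may already separate them.** This partly stands. A reader might infer that one-dose participants get no separate handling at all. In fact SAP 8 excludes the pre-3.0 group from a PP population whose definition and outputs cannot be read, and a cut-off line in the VAS section starts a rule that applies if at least 7 participants are single-dose. Neither can be called missing, and VAS may be dealt with. But readable SAP 10.13 and 10.14 put all efficacy analyses on ITT and all safety analyses on the Safety population. No readable text splits vital signs, injection-site findings, ODI or global assessment by doses received.

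**Pooling as randomized is correct for ITT.** This stands, and is why the pooled rows should remain.

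**The effect is small against noise.** This stands for VAS. With 24 per arm and an assumed SD of 20 to 30, the standard error of an arm difference is SD × √(2/24), about 5.8 to 8.7 points. A loss of 1.0 to 3.3 points is well inside that, in a trial not sized for power. It does not make the rows describe the right regimen.

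**The End of Study row is only an extra, and the groups are similar in time since last dose.** Both are true. The number of doses and the time since baseline still differ.

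**The information is available elsewhere.** SAP 10.4 and 10.9 count second doses and SAP 10.13.1 lists VAS by participant. That allows reconstruction, but the summary tables would not show it.

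**Conclusion.** The point holds in this form: the ITT and Safety by-visit rows at Days 120, 150 and 180 and the End of Study row blend one-dose and two-dose participants, and so do not describe the regimen in the objectives. Observed-value rows at Days 210 to 270 are not affected by planned Day 180 completers.

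The size cannot be fixed from the documents. It is a loss of 1.0 to 3.3 points out of an assumed 10-point dose-2 increment, if 7 to 24 of 72 are one-dose and spread evenly over arms. An uneven spread would add bias. The conclusion is firmest for vital signs, injection-site findings, ODI and global assessment, and open for VAS because of the unreadable rule. This is a cheap improvement to the tables, with no effect on the Day 270 summary of the primary efficacy endpoint.

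**What to change.** In SAP 7.5, drop the pooled End of Study row from by-visit summaries, since each value already falls in an analysis visit. Alternatively, split it into three labelled rows: Day 180, one dose; Day 270, two doses; early termination.

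In SAP 8, keep the pooled ITT and Safety rows. For Days 120, 150 and 180, add rows by number of doses received within each arm for vital signs, injection-site findings, ODI and global assessment. Add them for VAS too, unless the at-least-7 rule already does so. Label them descriptive and non-randomized.

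Split by doses received, not by protocol version. SAP 8 defines the pre-3.0 group by not having signed v3.0 consent, whereas SAP 10.4 also lists people who reconsented to v3.0, declined dose 2 and finish at Day 180.

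The cost is SAP wording and table shells, using dosing data already collected at Day 90. The downsides are a few more rows, small cells, and a split that is not a randomized comparison. It should be done before database lock, because SAP 7.2 treats later additions as post hoc.
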